^c If the observed DLT rate is $\geq 33\%$ in a cohort (eg, $\geq 33\%$ DLT-evaluable subjects experience DLT after receiving either 10^6 or 10^8 PFU/mL dose) or if the DLRT deem the dose intolerable in a cohort in the DLT evaluation period, then dose de-escalation or discontinuation of treatment with subsequent enrollment stop for that cohort will occur.

Approved

-
- ^d If dose de-escalation is needed and if permissible based on the incidence of DLTs, a minimum of **6** DLT-evaluable subjects will be enrolled and treated at a lower dose level of talimogene laherparepvec (Dose Level -1). The initial dose administered will be up to 4.0 mL of 10^6 PFU/mL followed by dose of up to 4.0 mL of 10^6 PFU/mL 21 days (+3 days) later. Subsequent doses of up to 4.0 mL of 10^6 PFU/mL will be administered 14 days (\pm 3 days) thereafter.
- ^e Treatment visits continue until the subject has achieved a complete response, all injectable tumors have disappeared, confirmed progressive disease per modified irRC RECIST, intolerance of study treatment, 24 months from the date of the first dose of talimogene laherparepvec, or need for alternative anticancer therapy, whichever occurs first.
- ^f If permissible based on the incidence of DLTs.
- ^g **Subjects will be followed for survival and use of subsequent anticancer therapies every 12 weeks (\pm 28 days) from the safety follow-up visit until death, subject or legally acceptable representative withdraws full consent/assent, or up to approximately 24 months after the last subject is enrolled in the study, whichever occurs first.**

Approved

Study Glossary

Abbreviation or Term	Definition/Explanation
ALT	alanine aminotransferase
ALP	alkaline phosphatase
ANC	absolute neutrophil count
ASR	age-standardized incidence rates
AST	aspartate aminotransferase
CI	confidence interval
CNS	central nervous system
CR	complete response
CRF	case report form
CT	computed tomography
CTCAE	Common Terminology Criteria for Adverse Events
DILI	drug-induced liver injury
DLRT	Dose Level Review Team
DLT	dose-limiting toxicity
DOR	duration of response
ECG	electrocardiogram
EDC	electronic data capture
End of Study for Individual Subject	Defined as the last day that protocol-specified procedures are conducted for an individual subject (ie, the date the subject withdraws full consent/assent from the study, completes the safety follow-up visit or long-term follow-up [whichever is later] or death).

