3. EXPERIMENTAL PLAN

3.1 Study Design

This is a phase 1, multicenter, open-label study of talimogene laherparepvec in pediatric subjects with advanced non-CNS tumors that are amenable to direct injection in the clinical setting. The overall study design is described by the [Study Design and Treatment Schema](#).

Approximately 18 to **24** pediatric subjects are expected to be enrolled **and treated with at least 1 dose of talimogene laherparepvec** into 2 cohorts stratified by age (permissible based on the incidence of DLTs, a minimum of 18 **dosed** subjects total **for the primary analysis**) as follows:

- Cohort A1 (12 to \leq 21 years of age)
- Cohort B1 (2 to $<$ 12 years of age)

Initially, 3 subjects 12 to \leq 21 years of age are to be enrolled and treated at 100% of the recommended adult dose regimen of talimogene laherparepvec (cohort A1). The first dose administered will be up to 4.0 mL of 10^6 PFU/mL followed by a dose of up to 4.0 mL of 10^8 PFU/mL 21 days (+ 3 days) later. Subsequent doses of up to 4.0 mL of 10^8 PFU/mL will be administered approximately every 14 days (\pm 3 days) thereafter (see [Section 6.2.1.1](#)). The DLT evaluation period is 35 days from the initial administration of talimogene laherparepvec. Rules for DLT evaluation are described in [Section 6.2.1.2.1](#). The dose level review team (DLRT) will review the safety data of the first 3 subjects in the older age cohort A1 to decide if the younger age cohort B1 can be opened for enrollment. If none of the first 3 DLT-evaluable subjects in cohort A1 experiences a DLT, then cohort B1 will be opened for enrollment and treatment at the same dose level per the [Study Design and Treatment Schema](#). If a DLT occurs in the first 3 DLT-evaluable subjects in the older age cohort (A1 or A2), the younger age cohort will not open until a DLT rate $<$ 33% is observed with at least 6 DLT-evaluable subjects in the older age cohort (A1 or A2). If any of the first 3 subjects in cohort A1 experiences a DLT, the DLRT will make a recommendation on whether an additional 3 subjects should be enrolled in cohort A1.

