Cohort A1 or B1 can enroll up to a maximum of **18 dosed** subjects **with at least 9 DLT-evaluable subjects in cohort A1**. In the case of dose de-escalation, the minimum number of DLT-evaluable subjects at the de-escalated dose will be **6** (permissible based on the incidence of DLTs). After an age cohort is closed for further enrollment, if $<$ 33% of all DLT-evaluable subjects in the cohort experiences a DLT at a

dose level (**minimum of 6 DLT-evaluable subjects**), the dose will be declared safe for the cohort.

If dose de-escalation is needed and if permissible based on the incidence of DLTs, a minimum of **6** additional DLT-evaluable subjects will be enrolled and treated at a lower dose level of talimogene laherparepvec (Dose Level -1). The initial dose administered will be up to 4.0 mL of 10^6 PFU/mL followed by dose of up to 4.0 mL of 10^6 PFU/mL 21 days (+3 days) later. Subsequent doses of up to 4.0 mL of 10^6 PFU/mL will be administered approximately every 14 days (\pm 3 days) thereafter (see [Table 1](#)). Dose de-escalation cohorts will obey the following naming convention, based on age at baseline, and the same DLT rules will be applied to the de-escalated cohorts:

- Cohort A2 (12 to \leq 21 years of age)
- Cohort B2 (2 to < 12 years of age)

Table 1. Dose De-escalation

Dose Level	Initial Dose	Subsequent Doses
1	10^6 PFU/mL	10^8 PFU/mL
-1	10^6 PFU/mL	10^6 PFU/mL

PFU = plaque-forming unit

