6.2.1.2 Dose-cohort Study De-escalation and Stopping Rules

Unlike conventional treatments, talimogene laherparepvec is administered directly into tumors and the dose is dependent on tumor size rather than subject's age, weight or body surface area. As the adult doses were safe and well-tolerated, this phase 1 study is designed with a dose de-escalation schema, which is described in detail in [Section 3.1 Study Design](#).

If the DLT is a serious herpetic event (eg, encephalitis, encephalomyelitis, or disseminated herpetic-like infection) caused by talimogene laherparepvec as

demonstrated by real-time polymerase chain reaction (qPCR) analysis, then the study will be terminated.

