6.2.1.2.1 Rules for DLT Evaluation

The DLT evaluation period is 35 days from the initial administration of talimogene laherparepvec. For a subject to be considered DLT-evaluable, subjects must receive 2 doses of talimogene laherparepvec (one dose of up to 4.0 mL of 10^6 PFU/mL followed by a dose of up to 4.0 mL of 10^8 PFU/mL for Dose Level 1, or 2 doses of up to 4.0 mL of 10^6 PFU/mL for Dose Level -1) during the 35 day DLT evaluation period, with the exception when a DLT occurs after the first dose. Subjects may be replaced in a cohort if they are not evaluable for DLT (ie, a subject did not receive at least 2 treatments of talimogene laherparepvec, or ended the study treatment before completion of DLT evaluation period for a reason other than experiencing a DLT).

A DLRT will review the safety data to evaluate possible drug effects and DLT. The DLRT will review the safety data of the first 3 DLT-evaluable subjects in the older age cohort (A1 or A2) to decide if the younger age cohort can be opened for enrollment. The decision to open the younger age cohort for subject enrollment will be based on < 33% DLT rate of the first 3 DLT-evaluable subjects in the older age cohort (A1 or A2) during the DLT evaluation period.

If a DLT occurs in the first 3 DLT-evaluable subjects in the older age cohort (A1 or A2), the younger age cohort will not open until a DLT rate < 33% is observed with at least 6 DLT-evaluable subjects in the older age cohort (A1 or A2). The starting dose for the younger age cohort will be Dose Level 1 (if the DLT rate in the older age cohort at Dose Level 1 is < 33%) or Dose Level -1 (if Dose Level 1 is intolerable for the older age cohort). After both cohorts are open, the DLRT will review the safety data after the earlier of the following events: (a) the addition of 3 new DLT-evaluable subjects in a cohort **until there're 9 DLT-evaluable subjects in the cohort**; (b) a DLT rate \geq 33% considering all DLT-evaluable subjects in a cohort; (c) at the occurrence of the first DLT in either cohort. **If deemed necessary, ad-hoc meetings to review the safety data can be convened anytime by the DLRT.**

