After an age cohort is closed for further enrollment, the dose will be declared safe for the cohort if the DLT rate at the dose level is < 33% (**minimum of 6 DLT-evaluable subjects**). If a DLT rate \geq 33% is observed at any time in a cohort or if it is deemed **unsafe** by the DLRT to continue **enrollment** in the cohort, the dose will be declared intolerable for the cohort. If permissible based on the incidence of DLTs, enrollment will

stop when 18 **dosed** subjects **evaluable for the primary analysis** have been confirmed across cohorts A1 and B1 except in the case of dose de-escalation when 6 additional DLT-evaluable subjects at Dose Level -1 will be needed (permissible based on the incidence of DLTs). Enrollment will not be halted while the DLT-evaluation period is still ongoing. During this time, investigators should contact the medical monitor to discuss the screening and enrollment of any potential subjects. However, enrollment may be halted for the following:

- if a DLT occurs in the older age cohort while both cohorts are enrolling subjects and before the younger age cohort reaches the first safety review, then further enrollment will be halted in the younger age cohort until a DLT rate < 33% is observed with at least 6 DLT-evaluable subjects in the older age cohort;
- if dose de-escalation occurs in any cohort while both cohorts are enrolling subjects.

The DLRT will consider the totality of available data across all cohorts in coming to any recommendation, including dose de-escalation, enrollment halt, opening or re-opening of cohort(s) for enrollment and/or the starting dose for the cohorts.

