6.2.1.2.2 Rules for Dose De-escalation

- If the observed DLT rate is $\geq 33\%$ in a cohort (eg, $\geq 33\%$ DLT-evaluable subjects experience DLT after receiving either 10^6 or 10^8 PFU/mL dose) or if the DLRT deem the dose intolerable in a cohort in the DLT evaluation period, then dose de-escalation or discontinuation of treatment with subsequent enrollment stop for that cohort will occur.
- In the case that dose de-escalation is needed, a minimum of **6** additional DLT-evaluable subjects will be enrolled at Dose Level -1 (permissible based on the incidence of DLTs)
- If the younger age cohort starts at Dose Level -1, no dose re-escalation will be considered.

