10.2 Sample Size Considerations

The sample size of **18 to 24 subjects will be enrolled and treated with at least 1 dose of talimogene laherparepvec including at least 9 DLT-evaluable subjects in cohort A1. For age cohort opening and dose de-escalation, criteria from 3+3 phase 1 design assuming a true DLT incidence rate < 33% is used. Sample size for cohorts with age between 2 and 12 years are not required.**

[figure not shown]
A dose level will be considered safe for a cohort if < 33% of all DLT-evaluable subjects in a given cohort experiences a DLT (**minimum 6 DLT-evaluable subjects**). [Table 5](#) and [Figure 1](#) presents the probability of declaring a dose level safe (unsafe) for a range of true DLT rates for the protocol therapy **based on 6 DLT-evaluable subject** (see triangle symbols in [Figure 1](#)). For example, the probability of declaring a dose level safe (unsafe) is 89% (11%), 42% (58%), and 11% (89%) if the true DLT rate is 10%, 30%, or 50%, respectively.

Table 5. Probability of Declaring a Cohort Safe or Unsafe

True Cohort DLT Probability	Probability Declare Cohort Safe	Probability Declare Cohort Unsafe
10%	89%	11%
20%	66%	34%
30%	42%	58%
40%	23%	77%
50%	11%	89%

Approved

Figure 1. Probability of Declaring a Cohort Safe (Unsafe)

DLT = dose-limiting toxicity

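### The stop at a 33% DLT rate has no minimum number of subjects, so 1 DLT in the first 3 ends a dose level that other sections and Table 5 carry on to 6

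*Protocol*

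**What the plan says.** **Text that stops the dose.** Protocol Section 6.2.1.2.1 makes the dose intolerable for the cohort if a DLT rate of at least "33% is observed at any time in a cohort or if it is deemed" unsafe by the DLRT to continue enrolling. Section 6.2.1.2.2 attaches the consequence: at 33% or more, "then dose de-escalation or discontinuation of treatment with subsequent enrollment stop for that cohort will occur". Footnote c of the Study Design and Treatment Schema repeats this, with DLRT judgment again as a second trigger ("if the DLRT deem the dose intolerable in a cohort in the DLT evaluation period, then dose de-escalation" or discontinuation follows). The minimum of 6 DLT-evaluable subjects in Section 6.2.1.2.1 belongs to the declaration that a dose is safe, not to the stop.

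**Text that continues to 6.**
- Protocol Section 3.1, repeated in SAP 3.1: "If any of the first 3 subjects in cohort A1 experiences a DLT, the DLRT will make a recommendation on whether an additional" 3 should be enrolled there. It names A1 only.
- Section 6.2.1.2.1: after a DLT in the first 3, the younger cohort stays closed "until a DLT rate < 33% is observed with at least 6 DLT-evaluable subjects in the older age cohort" (A1 or A2).
- Section 10.2, on cohort opening and de-escalation: "criteria from 3+3 phase 1 design assuming a true DLT incidence rate < 33% is used".
- Table 5 and SAP Table 2, based on 6 DLT-evaluable subjects: probability of declaring a cohort safe 89/66/42/23/11% at true DLT rates of 10/20/30/40/50%.

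**Text that links them.** Section 6.2.1.2 says "this phase 1 study is designed with a dose de-escalation schema, which is described in detail in" Section 3.1. Section 3.1 adds that "the same DLT rules will be applied to the de-escalated cohorts", listing A2 and B2. Section 10.3.2 plans a safety analysis after the first 3 evaluable subjects in each cohort, with a DLRT recommendation on 3 more, but bases that recommendation on the rules in Section 6.2.1.2.

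**The concern.** At exactly 1 DLT in the first 3, one set of sentences requires the cohort to stop or de-escalate and another expects it to continue to 6. Read literally, the stop is triggered even by 1 of 1 or 1 of 2.

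This outcome is an ordinary one in a phase 1 cohort, and the two instructions lead to different doses. In B1, the literal rule would either stop the cohort or move children aged 2 to under 12 to Dose Level -1, where subsequent doses are 10^6 instead of 10^8 PFU/mL (Table 1), a 100-fold lower concentration. In A2 and B2, Table 1 has no lower level, so enrollment would stop. A dose level could be abandoned under a rule that the stated operating characteristics do not describe, and two DLRT reviews could act differently on the same data.

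**Working it through.** **Inputs.** Threshold 33% (Sections 6.2.1.2.1 and 6.2.1.2.2, footnote c); reviews in steps of 3 evaluable subjects (Sections 6.2.1.2.1 and 10.3.2); 6 evaluable subjects and true DLT rates *p* from Table 5. Write *q* = 1 - *p*.

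**1. Is the trigger met?** 1/3 = 33.3%, which is at least 33%. The protocol reads it the same way: Section 6.2.1.2.1 opens the younger cohort if fewer than 33% of the first 3 have a DLT, and Section 3.1 expresses this as none of the first 3. At 6 subjects, 2/6 = 33.3% also meets the trigger. 1/4 = 25% and 1/5 = 20% do not.

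**2. Reproduce Table 5.** With 6 subjects and at most 1 DLT, P(safe) = q^6 + 6pq^5. At 10%: 0.5314 + 0.3543 = 0.8857. All five rows match the table. A classic 3+3 that accepts at 0 of 3, q^3 + 3pq^5, gives 90.6/70.9/49.4/30.9/17.2% and does not match from 20% upward. Table 5 is therefore a fixed binomial at n = 6. Stopping early at 2 DLTs leaves it unchanged, because a cohort with 2 DLTs by subject 6 fails anyway.

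**3. Apply the literal rule.** To reach 6 without triggering, a cohort needs 0 DLTs in the first 3 and at most 1 in the next 3: P(safe) = q^3 × (q^3 + 3pq^2). At 10%: 0.729 × 0.972 = 0.7086. Checking after every subject or only at 3 and 6 gives the same result.

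**4. The difference** is the path of 1 DLT in the first 3 followed by 0 in the next 3, which is 3pq^2 × q^3 = 3pq^5. Table 5 counts it as safe.

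| True DLT rate | Table 5 | If 1 of 3 expands | Literal rule | Difference (3pq^5) |
|---|---|---|---|---|
| 10% | 89% | 88.6% | 70.9% | 17.7 points |
| 20% | 66% | 65.5% | 45.9% | 19.7 points |
| 30% | 42% | 42.0% | 26.9% | 15.1 points |
| 40% | 23% | 23.3% | 14.0% | 9.3 points |
| 50% | 11% | 10.9% | 6.3% | 4.7 points |

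At a true rate of 10%, the probability of declaring the dose unsafe rises from 11% to 29%.

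**5. How often the instructions collide.** Exactly 1 of 3, 3pq^2, has probability 24/38/44/43/38% at 10/20/30/40/50%. The dose level is ended by the first 3 subjects with probability 1 - q^3 = 27/49/66/78/88% under the literal rule, against P(2 or more of 3) = 3/10/22/35/50% if 1 of 3 expands.

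**6. Consistency of the text.** If 1 of 3 made the dose intolerable, the condition in Section 6.2.1.2.1 (below 33% with at least 6 evaluable, after a DLT in the first 3) could never be met at that dose.

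**The case against.** **The specific rule governs the general one.** Section 3.1 and the waiting condition in Section 6.2.1.2.1 address a DLT in the first 3 directly, and Section 6.2.1.2 defers to Section 3.1. On that reading A1 and A2 expand. This is the more natural reading of intent, and it stands as such. But neither clause is worded as an exception to the mandatory stop, and the reading does not clearly reach B1 or B2.

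**Section 10.3.2 covers every cohort.** A reader might infer that the plan says nothing about B1 and B2. The documents do not support that: Section 10.3.2 speaks of each cohort, and Section 3.1 extends the DLT rules to B2 by name. However, Section 10.3.2 rests on the Section 6.2.1.2 rules, which contain the stop, and does not say what follows 1 of 3.

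**The DLRT weighs all the data.** Section 6.2.1.2.1 does say so for any recommendation. In the stopping sentences, though, DLRT judgment is an additional trigger, not a power to waive the 33% rule.

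**The schema may show the branch.** The figure was not available to this check, and a 1-of-3 branch drawn there could settle the intent. Footnote c would still contradict it.

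**The consequences are limited.** This stands. A1 had 10 subjects enrolled and B1 had 1 at Amendment 3, so the issue is live mainly for B1, which has no required size and may stay small, and for any A2 or B2. The literal rule errs toward stopping early. The primary summary in SAP 10.6.1, DLT incidence with an exact interval, does not use the rule.

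**Conclusion.** The plan is wrong as written and should be corrected. The stop at 33% has no minimum number of subjects, and in the available text nothing reconciles it with the continuation to 6 that Section 3.1, Section 6.2.1.2.1, the 3+3 criteria and Table 5 assume. The two readings give opposite final verdicts at n = 6 with probability 18/20/15/9/5% at true DLT rates of 10/20/30/40/50%.

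These figures assume independent DLTs at a constant rate in a new cohort that starts from zero and is followed to 6. The DLT status of B1's one enrolled subject is not given, and B1 may never reach 6.

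Two stronger conclusions do not follow. Table 5 is not miscalculated: it is correct for 6 subjects if 1 of 3 may expand. Nor does the conflict expose children to extra toxicity: the literal rule is the more cautious one, and its cost is a tolerable dose wrongly ended, or inconsistent decisions. That, and the narrow set of cohorts still affected, makes this a should-fix and not a bar to proceeding.

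**What to change.** In Section 6.2.1.2.1, Section 6.2.1.2.2 and schema footnote c, state that in every cohort (A1, A2, B1, B2):
- the 33% rule applies from 6 DLT-evaluable subjects;
- before then, 2 or more DLTs stop the dose;
- exactly 1 DLT in the first 3 expands the cohort to 6, unless the DLRT stops earlier.

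Keep the study-termination rule for serious herpetic events in Section 6.2.1.2. Align protocol Sections 3.1 and 10.3.2 and SAP 3.1, and check that the schema figure agrees.

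The cost is one sentence in three places and matching phrases in three more. The planned 18 to 24 subjects, Table 5, SAP Table 2 and the worked example are unchanged.

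If the sponsor intends the literal rule, remove the expansion wording and replace the safe probabilities in both tables with 71/46/27/14/6%. The worked example in the synopsis, Section 10.2 and SAP 3.2 then becomes 71% (29%), 27% (73%) and 6% (94%) at true rates of 10%, 30% and 50%.

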6.2.1.2.2 Rules for Dose De-escalation

- If the observed DLT rate is $\geq 33\%$ in a cohort (eg, $\geq 33\%$ DLT-evaluable subjects experience DLT after receiving either 10^6 or 10^8 PFU/mL dose) or if the DLRT deem the dose intolerable in a cohort in the DLT evaluation period, then dose de-escalation or discontinuation of treatment with subsequent enrollment stop for that cohort will occur.
- In the case that dose de-escalation is needed, a minimum of **6** additional DLT-evaluable subjects will be enrolled at Dose Level -1 (permissible based on the incidence of DLTs)
- If the younger age cohort starts at Dose Level -1, no dose re-escalation will be considered.

6.2.1.2.3 Definition of DLT

All toxicities will be graded using the CTCAE version 4.0 ([Appendix A](#)).

The occurrence of any of the following toxicities during the DLT evaluation period will be considered a DLT, if judged by the investigator to be related to the administration of talimogene laherparepvec:

- Grade 4 non-hematologic toxicity
- Grade 3 non-hematologic toxicity lasting > 3 days despite optimal supportive care
 - grade 3 fatigue will not be classified as DLT, irrespective of duration
- Any grade 3 or higher non-hematologic laboratory value if:
 - medical intervention is required, or
 - the abnormality leads to hospitalization, or

- the abnormality persists for > 1 week unless deemed not clinically important per both investigator and sponsor.
- Febrile neutropenia grade 3 or grade 4
- Thrombocytopenia < 25 x 10⁹/L associated with bleeding event requiring intervention
- Serious herpetic event:
 - herpetic encephalitis or disseminated herpetic infection
- Grade 5 toxicity (ie, death)
- Any other intolerable toxicity leading to permanent discontinuation of talimogene laherparepvec

If a subject experiences a DLT during the DLT evaluation period, study treatments will be discontinued for that subject.

Subjects who are in CR and no longer have injectable lesions will enter the 30-day safety follow-up and continue to have tumor assessments every 12 weeks for up to 24 months. Subjects who develop a new injectable lesion(s) within 12 months from the start date of treatment, but after all other injectable lesions have responded such that they are no longer injectable are eligible to restart treatment with talimogene laherparepvec under this protocol for up to a further 12 months. This includes subjects that achieve a CR and then develop a new injectable lesion.

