6.2.1.1 Dosage, Administration, and Schedule

Talimogene laherparepvec must be prepared and administered by a qualified healthcare professional. Subjects should be assessed clinically for adverse events/toxicity prior to each dose using the CTCAE version 4 ([Appendix A](#)). Complete blood count with differential and chemistry panels including liver function laboratory tests (ALT, AST, and total bilirubin) should be obtained according to the Schedule of Assessments ([Table 3](#)) and the results should be checked before each treatment. Dosing will occur only if these test values are acceptable per [Section 6.2.1.2](#) and [6.2.1.3](#). Sedation can be used and the type and dose is up to the discretion of the investigator taking into consideration the subject's medical history, age, and site of disease. Additionally, use of pain medication (eg, acetaminophen/paracetamol/narcotic) or anti-anxiety medication (eg, benzodiazepine) as premedication to help decrease the pain or anxiety associated with the injection is acceptable and left to the discretion of the investigator. Because

flu-like symptoms are common adverse events experienced by HSV-seronegative subjects after talimogene laherparepvec treatment, premedication with the appropriate antipyretic and/or antiemetic medications prior to each talimogene laherparepvec treatment is strongly recommended to prevent the occurrence of these symptoms in the HSV-seronegative subjects. The type and dose will be up to the discretion of the investigator taking into consideration the subject's medical history and age.

Talimogene laherparepvec will be administered by intralesional injection only into injectable cutaneous, subcutaneous, nodal tumors, and other non-visceral tumors with or without image guidance. Talimogene laherparepvec must not be administered into tumor lesions in visceral organs.

The first dose of talimogene laherparepvec will be up to 4.0 mL of 10^6 PFU/mL administered on day 1. The second injection, up to 4.0 mL of 10^8 PFU/mL (or up to 4.0 mL of 10^6 PFU/mL for a dose de-escalated cohort), will be administered 21 (+ 3) days after the initial injection (ie, no sooner than day 22 but should not be delayed more than 3 days after the 21-day time point). All subsequent injections, up to 4.0 mL of 10^8 PFU/mL (or up to 4.0 mL of 10^6 PFU/mL for a dose de-escalated cohort), will be administered every 14 (\pm 3) days. The treatment cycle interval may be increased due to toxicity.

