7. STUDY PROCEDURES

7.1 Schedule of Assessments

For Schedule of Assessments please refer to [Table 3](#).

Approved

Table 3. Schedule of Assessments

Period	Screening (≤ 28 days)	Treatment ^{a, d}																			Safety Follow-up ^b	Long-term Follow-up ^c Every 12 weeks	
		1	2	4	5	6	8	10	12	14	16	18	20	22	24	26	28	30	32 ^d				
Week		1	1	1	2	2	2	3	4	5	6	7	8	9	10	11	12	13	14	15	16		
Talimogene Laherparepvec Cycle		1	1	1	2	2	2	3	4	5	6	7	8	9	10	11	12	13	14	15	16		
Day		1	2	8	22	23	29	36	50	64	78	92	106	120	134	148	162	176	190	204	218		
General Assessments^d																							
Informed consent/assent	X																						
Review of eligibility criteria	X																						
Demographics, medical, surgical and medication history	X																						
Physical exam		X							X				X				X				X	X	
Vital signs ^e		X			X			X	X	X	X	X	X	X	X	X	X	X	X	X	X	X	
Body weight		X							X				X				X				X	X	
Height		X																					
Performance status ^f	X	X							X				X				X				X	X	
Recording of concomitant medications	X	X	X	X	X	X	X	X	X	X	X	X	X	X	X	X	X	X	X	X	X	X	X ^g
12-lead ECG	X																						
Review of adverse events, disease-related events and serious adverse events		X	X	X	X	X	X	X	X	X	X	X	X	X	X	X	X	X	X	X	X	X	X ^h
Survival assessment																							X

Approved

Footnotes defined on last page of the table.

Table 3. Schedule of Assessments

Period	Screening (≤ 28 days)	Treatment ^a																			Safety Follow-up ^b	Long-term Follow-up ^c Every 12 weeks	
		1	2	4	5	6	8	10	12	14	16	18	20	22	24	26	28	30	32 ^d				
Week		1	1	1	2	2	2	3	4	5	6	7	8	9	10	11	12	13	14	15	16		
Treatment Cycle		1	1	1	2	2	2	3	4	5	6	7	8	9	10	11	12	13	14	15	16		
Day		1	2	8	22	23	29	36	50	64	78	92	106	120	134	148	162	176	190	204	218		
Local Laboratory Tests																							
Chemistry ^d	X	X			X			X		X		X		X		X		X		X		X	
Hematology ^d	X	X			X			X		X		X		X		X		X		X		X	
Hepatitis B surface antigen and Hepatitis B core antibody	X																						
Hepatitis C virus antibody	X																						
PT or INR and PTT or aPTT	X																						
Urine pregnancy test ⁱ		X ^j																				X	
Central Laboratory Tests																							
Blood for HSV serostatus ^k	X							X														X	

Approved

Footnotes defined on last page of the table.

Table 3. Schedule of Assessments

Period	Screening (≤ 28 days)	Treatment ^a																			Safety Follow-up ^b	Long-term Follow-up ^c		
		1	2	4	5	6	8	10	12	14	16	18	20	22	24	26	28	30	32 ^d	Every 12 weeks				

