^d Subjects undergoing talimogene laherparepvec treatment beyond week 32 should continue general study assessments and local laboratory tests until the end of treatment (vital signs, recording of concomitant medications and review of adverse events, disease-related events and serious adverse events, [REDACTED], physical exam, body weight and performance status every fourth cycle and chemistry and hematology every second cycle). Exposure of subject's household member or caregiver and healthcare provider should continue to be checked at every cycle.

^e Vital signs (blood pressure, heart rate, respiration rate, and temperature) to be collected predose.

^f Karnofsky performance status will be used for subjects aged 12 to \leq 21 years; Lansky play scale will be used for subjects aged 2 to < 12 years.

^g Only anticancer therapies will be collected/recorded every 12 weeks during the long-term follow-up.

^h Talimogene laherparepvec related adverse events.

ⁱ Female subjects of childbearing potential only. A female is considered of childbearing potential (ie, fertile), following menarche and until becoming post-menopausal unless permanently sterilized. Permanent sterilization methods include hysterectomy, bilateral salpingectomy and bilateral oophorectomy.

^j To be performed within 72 hours prior to dosing.

^k Blood sample for HSV serostatus will be performed at a local laboratory at screening and at a central laboratory thereafter.

^m Blood draw for real-time polymerase chain reaction (qPCR) testing of talimogene laherparepvec DNA will be performed at the following time points:

- day 1 (prior to and approximately 1 hour [\pm 15 minutes] and 4 hours [\pm 30 minutes] after talimogene laherparepvec administration), day 2 approximately 24 hours [\pm 30 minutes] after talimogene laherparepvec administration, day 8 (\pm 2 days), day 22 (prior to and approximately 1 hour [\pm 15 minutes] and 4 hours [\pm 30 minutes] after talimogene laherparepvec administration), day 23 approximately 24 hours [\pm 30 minutes] after talimogene laherparepvec administration, day 29 (\pm 2 days), day 36 (\pm 2 days) prior to dosing, and day 50 (\pm 2 days) prior to dosing.

Approved

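### Table 3 takes no chemistry or hematology between Days 1 and 22 or between Days 22 and 36, so a silent laboratory DLT defined by lasting more than one week can go unseen or unconfirmed

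*Protocol*

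**What the plan says.** Protocol 6.2.1.2.3 makes a related grade 3 or higher non-hematologic laboratory value a DLT in three situations: it needs medical intervention, it leads to hospitalization, or "the abnormality persists for > 1 week unless deemed not clinically important per both investigator and sponsor". The third condition can be met by a child with no symptoms.

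Protocol 6.2.1.2.1 sets the window: "The DLT evaluation period is 35 days from the initial administration of talimogene laherparepvec".

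In Table 3, under "Local Laboratory Tests", chemistry and hematology are marked at screening and on Days 1, 22, 36 and 64, then every second cycle. The visits on Days 2, 8, 23 and 29 carry adverse-event review but no panel. Beyond week 32, footnote d continues "chemistry and hematology every second cycle". Footnote m opens "Blood draw for real-time polymerase chain reaction (qPCR) testing of talimogene laherparepvec DNA will be performed at the following time points", and its list includes Days 8 and 29.

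Protocol 6.2.1.1 has the panels obtained as Table 3 schedules them and adds that "the results should be checked before each treatment".

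**The concern.** A criterion that depends on persistence needs serial values, and the schedule does not supply them inside the DLT window. Subject incidence of DLTs is the primary endpoint. It decides whether the younger cohort opens, whether the dose is de-escalated, and whether a dose is declared safe. A laboratory DLT that nobody measures is counted as no DLT, so the error runs in one direction only: a lower observed rate and a higher chance of declaring the dose safe. Protocol Table 5, which gives those chances, implicitly assumes that every DLT is ascertained.

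**Working it through.** **Day count.** Protocol 6.2.1.1 places the second injection 21 days after the first, "no sooner than day 22 but should not be delayed more than 3 days after the 21-day time point". So 21 days after the first dose is Day 1 + 21 = Day 22, and on the same count the window closes on Day 1 + 35 = Day 36. Protocol 7.2.2 puts dosing after the other procedures at a visit, so the Day 22 and Day 36 panels are both pre-dose.

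**Schedule.** The dosing row of Table 3, read by the same columns, lands on Days 1, 22, 36, 50 and every 14 days after. This confirms the alignment of the laboratory rows. The gaps are 22 - 1 = 21 days and 36 - 22 = 14 days, against a criterion of more than 7 days.

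**Table 5 first.** With 6 evaluable subjects, safe means at most 1 DLT (2/6 is at least 33%). P(safe) = (1-p)^6 + 6p(1-p)^5 gives 88.6, 65.5, 42.0, 23.3 and 10.9% at true rates of 10 to 50%. Table 5 prints 89, 66, 42, 23 and 11%, so it is reproduced.

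**Chance that a scheduled sample meets the abnormality.** Assumptions, not from the documents: no symptoms, uniform onset, and a duration of 8 days, the shortest whole number above one week. Onset on Day d means present on Days d to d+7.

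- *Onset Days 2-21 (20 days).* Day 22 meets it if d+7 ≥ 22, so d = 15-21: 7 of 20. A Day 8 sample adds d = 2-8: 14 of 20.
- *Onset after the second dose (given on Day 22).* To have lasted more than 7 days by the Day 36 pre-dose sample requires 36 - d > 7, so d = 23-28 (6 days). These abnormalities end on Days 30-35. Day 36 meets 0 of 6; a Day 29 sample would meet 6 of 6.
- *Borderline.* Onset on Day 29 is exactly 7 days old on Day 36. If it is counted as qualifying, Day 36 meets 1 of 7 and Day 29 meets 7 of 7.
- *Longer duration (13 days, present on d to d+12).* Day 22 meets d = 10-21, 12 of 20 (19 of 20 with Day 8). Day 36 meets d = 24-28, 5 of 6.

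**Detection is not confirmation.** After the second dose the window holds at most one scheduled panel, Day 36, and one value cannot show a duration. Days 22, 29 and 36 are exactly 7 days apart, so adjacent samples do not show more than one week either. With the 3-day visit allowance in Protocol 7.2, the Day 36 panel can fall on Days 33-39. If the second dose is on Day 25, the third falls on Days 36-42 (25 + 14 ± 3).

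**Effect on the decision rule (range only).** Let m be the share of all DLTs missed, and replace p by p(1-m). At a true rate of 30%:

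| m | p(1-m) | P(declare safe) |
|---|---|---|
| 0 | 0.300 | 42% |
| 10% | 0.270 | 49% |
| 25% | 0.225 | 59% |
| 50% | 0.150 | 78% |

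The documents do not give m. For scale, if 13 of 20 (65%) silent 8-day abnormalities are unsampled, m = 10% needs about 0.10/0.65 = 15% of all DLTs to be of this kind. For m = 25% the figure is 38%, and for m = 50% it is 77%.

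**The case against.** **A reader might infer that every laboratory DLT after the first 10^8 dose goes unmeasured.** The documents do not support that.

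- On the protocol's own count Day 36 closes the window and is sampled. Of all 8-day onsets on Days 23-35, it meets those on Days 29-35, which is 7 of 13. A count of 0 of 13 needs a window read as Days 1-35, which the protocol does not state.
- Laboratory DLTs that required intervention or hospitalization are known by definition. Febrile neutropenia and thrombocytopenia with bleeding present clinically, and adverse events are reviewed on Days 2, 8, 22, 23, 29 and 36.

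**The exposed class is narrow and probably uncommon.** The event must be related to treatment, and it drops out if investigator and sponsor both judge it unimportant. In the pivotal adult trial, cellulitis was the only grade 3 or 4 event in at least 2% of treated patients (Protocol 2.2.2). The Amendment 3 rationale reports no known serious effect on marrow or liver. This is a fair argument for a small effect. However, Protocol 2.3 says that incidence and severity in children are unknown, and Protocol 6.2.1.3 notes immune-mediated glomerulonephritis in earlier trials.

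**Repeat tests and dose delays exist.** Appendix A asks for repeat liver tests within 24 hours once AST or ALT exceeds 3x ULN, and Protocol 6.2.1.3 delays dosing for related grade 3 toxicity. Both act only after an abnormality is known, so they do not close the gap.

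**Eight days is close to the worst case.** That is correct, and the 13-day figures show how quickly the loss shrinks.

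**A reader might also see a contradiction between 6.2.1.1 and Table 3**, because no panel is scheduled for the doses on Days 50, 78, 106 and so on. But the same sentence in 6.2.1.1 defers to Table 3 for when the panels are obtained, and checking the latest scheduled result would satisfy it. This is an ambiguity, and those days lie outside the DLT window.

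**Conclusion.** The point holds in a narrow form. A related, silent, grade 3 or higher non-hematologic laboratory abnormality that qualifies only by lasting more than one week can begin and end between scheduled panels. If it begins after the second dose, scheduled samples within the window cannot establish its persistence. Under the 8-day, uniform-onset assumption, the schedule meets 35% of onsets in the first gap. It meets none of the post-second-dose onsets that can exceed a week by Day 36. Counting Day 36 as inside the window does not change this second result.

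The bias favors declaring the dose safe. Its size cannot be stated, because the documents give neither the frequency nor the duration of such events. The 49% to 78% range is a sensitivity calculation and not an estimate; its upper end would need most DLTs to be of this one kind. Table 5 is arithmetically right but conditional on complete ascertainment. The change is worth making because it improves measurement of the primary endpoint at little cost. The design does not fail without it.

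**What to change.** 1. In Table 3, add local chemistry and hematology to the existing Day 8 and Day 29 visits, drawn with the qPCR sample that footnote m already schedules.
2. Require a repeat test more than 7 days after any first grade 3 or higher non-hematologic laboratory value, so that persistence can be determined. A first value on Day 29 puts that repeat on Day 37 at the earliest (29 + 8). The text should therefore also say how an abnormality that begins inside the window but is confirmed after it is classified, and how one that has resolved by the repeat is classified.
3. State whether the Day 36 pre-dose sample counts as inside the DLT window.
4. Give these results to the DLRT.
5. Separately, clarify whether the check before each treatment in 6.2.1.1 refers to the latest scheduled result or to a new sample, given the every-second-cycle panels in Table 3 and footnote d.

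The cost is two small local panels per child (a few mL of blood) at visits and draws that already take place, plus any triggered repeats. The observed DLT rate may rise slightly.
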